#### **12.1.10 Adverse Events of Special Interest**

Treatment-emergent nausea (preferred term), vomiting (preferred term), insomnia (defined below), and sexual dysfunction (defined below) will be summarised. TEAE related to the musculoskeletal SOC will be summarized.

Insomnia related adverse events and sexual dysfunction related adverse events are defined in [Panel 4](#) and [Panel 5](#).

---

#### **Panel 4    Insomnia related adverse events searches**

---

##### **Preferred term**

---

Hyposomnia  
Initial Insomnia  
Insomnia  
Middle Insomnia  
Poor Quality Sleep  
Sleep Disorder  
Terminal Insomnia  
Dyssomnia

---

**Panel 5 Sexual dysfunction related adverse events searches**

Preferred Term		
Anorgasmia	Genital hypoesthesia	Kluver-Bucy syndrome
Ejaculation delayed	Persistent genital arousal disorder	Libido increased
Ejaculation failure	Adrenal androgen deficiency	Luteinising hormone deficiency
Female orgasmic disorder	Adrenal androgen excess	Masochism
Female sexual arousal disorder	Adrenogenital syndrome	Mauriac syndrome
Libido decreased	Albright's disease	Nocturnal emission
Loss of libido	Compulsive sexual behaviour	Painful ejaculation
Male orgasmic disorder	Delayed puberty	Painful erection
Orgasm abnormal	Erection increased	Paraphilia
Orgasmic sensation decreased	Excessive masturbation	Precocious puberty
Premature ejaculation	Excessive sexual fantasies	Priapism
Vulvovaginal dryness	Exhibitionism	Primary ciliary dyskinesia
Disturbance in sexual arousal	Fertility increased	Primary hypogonadism
Dyspareunia	Fetishism	Pseudoprecocious puberty
Ejaculation disorder	Follicle stimulating hormone deficiency	Psychosexual disorder
Erectile dysfunction	Frotteurism	Pubertal failure
Female sexual dysfunction	Gender dysphoria	Retrograde ejaculation
Genito-pelvic pain/penetration disorder	HAIR-AN syndrome	Sadism
Inadequate lubrication	Hyperandrogenism	Spontaneous ejaculation
Libido disorder	Hypergonadism	Spontaneous penile erection
Male sexual dysfunction	Hyperoestrogenism	Transvestism
Organic erectile dysfunction	Hyperprogesteronism	Voyeurism
Psychogenic erectile dysfunction	Hypersexuality	Paedophilia
Sexual aversion disorder	Hypogonadism	Post-sterilisation regret
Sexual dysfunction	Hypoprogesteronism	
Sexual inhibition	Incomplete precocious puberty	

The second and third column represent the preferred terms that has been added based on a post-marketing request by EMA.

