1.1.3.3 Safety

The evaluation of the safety and tolerability of vortioxetine is based on data from a large clinical development programme. In the completed Phase II to IV short- and long-term studies in adults, more than 8000 patients with MDD or Generalized Anxiety Disorder (GAD) received vortioxetine at doses of 1 to 20 mg/day, corresponding to an overall exposure >3200 patient-years. Overall short- and long-term treatment with vortioxetine at the therapeutic doses (5-20 mg/day) was safe and well tolerated in adults and in the elderly. The incidence of nausea, the most common adverse event (AE), showed a trend towards a dose-response relationship. For vortioxetine, at the therapeutic doses, the incidences of adverse events such as insomnia, somnolence, fatigue, and hyperhidrosis, were at placebo level, as was the incidence of sexual dysfunction. The changes in body weight, vital signs, ECGs (including the QTc interval), and clinical safety laboratory tests (including liver and renal tests) were at placebo level for all therapeutic doses of vortioxetine. Abrupt discontinuation of vortioxetine after short, as well as after long-term treatment was well tolerated. Based on an 8-week vortioxetine study, the direct switch from \geq 6-week treatment with selective serotonin reuptake inhibitor/serotonin-norepinephrine reuptake inhibitor (SSRI/SNRI) to vortioxetine was well tolerated.

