5.2 Selection Criteria

Patients will be recruited among those who complete treatment in Study 12709A or 12710A.

Patient selection is based on the inclusion and exclusion criteria listed below.

Patients who meet each of the inclusion criteria and none of the exclusion criteria at the Baseline Extension A Visit of this extension study are eligible to participate in this study. However, the sponsor reserves the right to utilise quality oversight methods to determine appropriateness of patient enrolment into the study.

Inclusion Criteria

1. The patient is a male or female child aged ≥ 7 and <12 years or adolescent aged ≥ 12 and ≤ 18 years at Baseline Extension A.
2. For patients aged ≥ 7 and ≤ 17 years at the Baseline Extension A visit; the patient is able to understand the Informed Assent Form, and parent(s)/legal representative(s)/ are able to read and understand the Informed Consent Form.
3. For patients aged ≥ 7 and ≤ 17 years at the Baseline Extension A visit; The patient has provided a new assent to participation (signed the new informed assent form) and parent(s)/legal representative(s) signed the new Informed Consent Form which are separate from the informed assent/consent obtained from patient and parent(s)/legal representative(s) for Study 12709A or 12710A.
4. For patients aged 18 at the Baseline Extension A visit; the patient is able to read and understand the Informed Consent Form.

5. For patients who turned 18 years during the lead-in study 12710A; the patient has signed the Informed Consent Form.
6. The patient and parent(s)/ legal representative(s) are willing and able to attend study appointments within the specified time windows. For patients who turned 18 years during the lead-in study 12710A; the patient is willing and able to attend study appointments within the specified time windows.
7. The patient must have completed Study 12709A or 12710A (Visit 12, Completion Visit) immediately prior to enrolment into this extension study.
8. The patient had a primary diagnosis of a Major Depressive Disorder (MDD) at entry in Study 12709A or 12710A, diagnosed according to DSM-5™.
9. The patient is indicated for long-term treatment with vortioxetine according to the clinical opinion of the investigator.
10. The patient, if a female of childbearing potential (defined as girls aged ≥ 10 years old and younger girls who, at the discretion of the investigator, are deemed to be of reproductive potential) and sexually active, must:

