
The blood and urine drug screen samples will be analysed at the central laboratory.

The additional urine samples will be collected and analysed at the site using dipsticks. If the dipstick evaluation is positive or abnormal, further analysis will be performed at the central laboratory.

The investigator must review (initial and date) the results of the clinical safety laboratory tests as soon as possible after receipt of those results. Out-of-range values must be interpreted by the investigator as “not clinically significant” or “clinically significant” with a comment concerning the planned follow-up. Tests for clinically significant out-of-range values must be repeated, or an appropriate clinical follow-up must be arranged by the investigator and documented on the laboratory report, until the value has stabilised or until the value has returned to a clinically acceptable value (regardless of relationship to IMP). Any value that is out-of-range at the Completion or Withdrawal Visit and judged clinically significant must be followed according to accepted medical standards for up to 30 days or until the value normalises or stabilises or a diagnosis or reasonable explanation has been established. Any out-of-range values followed after the last protocol-specified contact with the patient will be documented in the patient’s medical record.

Clinically significant out-of-range values must be recorded as an adverse event on an *Adverse Event Form*.

The central laboratory will be notified by the sponsor when the biological samples may be destroyed.

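### The sexual dysfunction event of special interest pools pubertal, endocrine and paraphilia terms without separate rows, so its incidence can include events that are not sexual dysfunction

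*SAP*

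**What the plan says.** SAP 12.1.10 lists the events of special interest: "Treatment-emergent nausea (preferred term), vomiting (preferred term), insomnia (defined below), and sexual dysfunction (defined below) will be summarised". Sexual dysfunction is defined by Panel 5, a three-column list of preferred terms. The note beneath it reads: "The second and third column represent the preferred terms that has been added based on a post-marketing request by EMA". The added columns include terms such as "Delayed puberty" and "Follicle stimulating hormone deficiency". Neither 12.1.10 nor Panel 5 specifies a subgroup of terms, a core list, or a split by age or sex. SAP 12.1.1 gives sex-specific denominators for single sex-specific terms but does not mention a group that mixes them.

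Protocol 5.2 admits a "child aged ≥ 7 and <12 years or adolescent aged ≥ 12 and ≤ 18 years at Baseline Extension A". Panel 4 of the protocol lists estradiol (girls), total testosterone (boys), LH, FSH, LHRH and prolactin. Protocol 9.4.2 has the hormones sampled at Visit 1 with a separate kit and says: "Clinically significant out-of-range values must be recorded as an adverse event on an" Adverse Event Form. Tanner stage is scheduled at baseline, Week 12 and completion, and is itself listed under the primary safety endpoint.

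**The concern.** One label covers at least two safety questions. Whether vortioxetine impairs sexual function is one. Whether it disturbs puberty or reproductive hormones is another, and it has particular weight in this age range. A single pooled incidence answers neither cleanly. A few pubertal or endocrine diagnoses would raise the sexual dysfunction figure, and the same few would be hard to see inside it.

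This study looks for such disorders through staging and hormone tests, so the added terms have a route into the count here.

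**Working it through.** **1. Counting Panel 5.** The documents give no incidence or threshold for this event, so there is no stated figure to reproduce. Classifying each term by its wording gives:

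| Group | Col. 1 | Col. 2 | Col. 3 | Total |
|---|---|---|---|---|
| Column 1 | 26 | – | – | 26 |
| Pubertal or reproductive-endocrine | 0 | 14 | 6 | 20 |
| Paraphilias | 0 | 3 | 6 | 9 |
| Added terms that plainly describe sexual function | 0 | 2 | 5 | 7 |
| Other added terms | 0 | 7 | 7 | 14 |
| All | 26 | 26 | 24 | 76 |

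- Added terms: 50/76 = 66%. Pubertal or endocrine: 20/76 = 26%. Paraphilias: 9/76 = 12%. These are shares of terms, not of patients.
- The 20 fall to 18 (5 pubertal, 13 hormonal) if Albright's disease and Mauriac syndrome are left out, hence about 20.
- The seven sexual-function terms are genital hypoesthesia, persistent genital arousal disorder, libido increased, painful ejaculation, retrograde ejaculation, painful erection and priapism.
- The other 14 include primary ciliary dyskinesia, post-sterilisation regret, gender dysphoria and nocturnal emission.

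**2. How a finding could enter the count.**

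- Protocol 9.4.1 makes a test result an adverse event only if the investigator judges it clinically significant. The SAP's table of potentially clinically significant laboratory limits covers prolactin and TSH but not estradiol, testosterone, LH or FSH, so for those four there is no listed limit beside that judgement.
- Protocol 10.3 prefers a diagnosis to signs, and has out-of-range values that belong to one condition recorded under one diagnosis. About seven of the hormonal terms could follow from an analyte on the panel: FSH deficiency, LH deficiency, hyperoestrogenism, hyperandrogenism, hypogonadism, primary hypogonadism and hypergonadism.
- SAP 12.1.2.3 counts events from Visit 1 itself as treatment-emergent, whereas Protocol 17.10.1 counts from the date of first dose. SAP chapter 17 declares a change but words it as after Visit 1. Under the 12.1.2.3 wording, a diagnosis from the baseline hormone sample dated to Visit 1 would count.

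**3. Size per patient.** Planned N is about 850. The SAP's inputs give 1200 × 0.85 × 0.85 = 867 at 15% lead-in withdrawal and 1200 × 0.80 × 0.85 = 816 at 20%. One patient is 1/850 = 0.12 percentage points, and also 0.12 at either end of that range.

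**4. Illustration with assumed rates.** Suppose 1% of patients have a Panel 5 event outside the pubertal, hormonal and paraphilia terms, a proportion x have one inside them, and the two are independent. Then pooled incidence = 1 − (1 − 0.01)(1 − x), and the share due to those terms = (pooled − 0.01)/pooled.

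| x | Pooled incidence | Share due to those terms |
|---|---|---|
| 0% | 1.00% | 0% |
| 0.2% | 1.20% | 17% |
| 0.5% | 1.50% | 33% |
| 1% | 1.99% | 50% |

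Neither the 1% nor any value of x comes from the documents.

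**The case against.** The strongest reply is that the groups can already be separated. SAP 12.1.5 tabulates treatment-emergent events by preferred term, all adverse events are listed, and the panel's note shows which columns were added. Puberty has its own outputs: Tanner shift tables, menstrual summaries, and laboratory values by visit. The primary objective rests on an overall clinical evaluation, with no test or threshold on this event. All of that is correct, and it makes this a matter of presentation. But rows by preferred term cannot be added into a patient-level rate, because one patient may have several terms.

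A second reply is that the list follows an EMA request whose text is not available, so the reporting format EMA wanted is unknown. That is a reason to keep the full total; it does not prevent further rows.

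A reader might also infer that the reported incidence will in part be a count of puberty and laboratory findings. The documents do not support that. Normal puberty is not an adverse event, and the five pubertal terms are disorders. Panel 5 has no terms for a raised or lowered hormone value, so a result coded that way would not be captured. Prolactin is measured but has no Panel 5 term.

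Nor do the documents plan a comparison with the adult programme. Protocol 1.1.3.3 says of adult adverse events that several "were at placebo level, as was the incidence of sexual dysfunction", but this is background, and the list behind it is not given.

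**Conclusion.** The pooling is real, and no row specified in the SAP gives an interpretable sexual dysfunction incidence. The pooled figure can include events that are not sexual dysfunction. It is not established that it will, and zero is a plausible number over 26 weeks. The only size that follows from the documents is 0.12 percentage points per patient at 850 treated. A specific inflation, such as half a point or one point, would need an event rate that neither document gives.

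The conclusion rests on a classification of terms by their wording, which moves the pubertal and endocrine count between 18 and 20 without changing the point. It also assumes that summarising sexual dysfunction means one grouped count, as 12.1.10 reads.

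It would be equally wrong to equate sexual dysfunction with column 1. The added columns hold genuine sexual-function terms, such as retrograde ejaculation, priapism and genital hypoesthesia, and leaving them out would bias the figure downward.

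**What to change.** Keep the full Panel 5 total as listed, and add to SAP 12.1.10 counts of patients with at least one event in each of these groups:

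- (a) sexual-function terms: column 1 plus the added terms that describe sexual function, with the seven named above as the starting set; column 1 alone is also shown, as the list before the EMA addition;
- (b) pubertal and reproductive-endocrine terms;
- (c) the remaining added terms, including the paraphilias.

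State the denominator for these mixed-sex groups. Base statements on sexual dysfunction on row (a), and read row (b) with the Tanner and hormone results.

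The cost is a slightly longer table and an allocation of terms to groups fixed in advance. Some of the 14 other added terms, such as hypersexuality or spontaneous ejaculation, need a clinical decision on where they belong. No new data are needed, and nothing in the requested list is lost.

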## 12.2 General Methodology for Other Safety Data

Unless otherwise specified, tables, graphs, and listings will be based on the APTS, and the tables will be presented for all patients and by lead-in study and by lead-in treatment.

The denominators for the summaries of a given variable will be based on the number of patients with non-missing values at a given visit or during the assessment period.

Descriptive statistics for the safety variables, both absolute values and change from baselines (baseline at randomisation in lead-in study and OLEXA), will be presented by visit and for the last assessment. All available post-OLEXA assessments will be included in the identification of the last assessment.

The number and percentage of patients with at least one PCS value at any post-baseline assessment time point will be summarized by variable. All available assessments will be included in the evaluation of PCS values.

The number and percentage of patients with values out-of-reference range and/or PCS range will be summarized by variable, visit, and last post-baseline assessment.

For patients with post-baseline PCS values, listings will be provided including all the values for those patients for the variable, with flagging of PCS values and out-of-reference-range values.

The PCS definition will be provided by H. Lundbeck and are stated in [Appendix IV](#).

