9.4.2 Clinical Safety Laboratory Tests

The clinical safety laboratory tests are listed in [Panel 4](#).

Results of safety laboratory tests for Visit 12 (Completion Visit) of the lead-in studies 12709A or 12710A will be transcribed to Visit 1 (Baseline Extension A) of 12712A study (i.e. these tests should not be collected at Visit 1). However, the Hormones laboratory tests are specific for the 12712A study and will be collected at the 12712A Visit 1 using a separate kit.

Panel 4 Clinical Safety Laboratory Tests

Haematology B-haemoglobin B-erythrocyte count B-haematocrit B-total leucocyte count B-neutrophils (% of total leucocytes) B-eosinophils (% of total leucocytes) B-basophils (% of total leucocytes) B-lymphocytes (% of total leucocytes) B-monocytes (% of total leucocytes) B-thrombocyte count	Electrolytes^a S-sodium S-potassium S-calcium (total)	Urine^b U-protein (dipstick) U-glucose (dipstick) U-blood (dipstick) U-ketones (dipstick)	
		Endocrine and Metabolic^a S-albumin S-glucose (non fasting)	
		Kidney^a S-creatinine S-urea nitrogen (BUN)	
	Hormones S-estradiol (girls) S-total testosterone (boys) S-LH S-FSH S-LHRH S-prolactin S-TSH ^c	Urine Drug Screen^e U-amphetamines (incl. methamphetamine) U-barbiturates U-benzodiazepines U-cannabinoids U-cocaine U-opiates U-phenocyclidine	
		Blood Alcohol Screen^e B-ethanol	
		Infection S-C-reactive protein (CRP)	
	Serology^c B-HBsAg B-anti HCV		
B – blood; P – plasma; S – serum; U – urine			

 a. Clinical chemistry b. Microscopic examination (leucocytes, erythrocytes, and casts) will be performed only if any of the urine evaluations are abnormal. c. TSH and hepatitis B and C panels are optional and may be performed at the investigator's discretion if there is clinical justification. d. Females >10 years of age or female patients at lower age judged by the investigator to be of childbearing potential. Additional pregnancy tests during the study will be performed according to local requirements. Females under 11 years will be tested with a urine hCG test and females over 11 years will be tested with using a blood hCG test. e. It is not mandatory to screen for drugs and/or alcohol. However, it can be performed at any visit, at the discretion of the investigator. 			

Blood samples for the clinical safety laboratory tests will be collected as outlined in [Panel 2](#). The blood sampling and handling procedures are described in the study-specific *Laboratory Specification Manual*.

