17.10.2 Analyses of Safety Endpoints

Adverse events, PAERS items, Tanner scores, clinical safety laboratory tests, vital signs, height, weight, BMI, and ECG parameters will be summarised, and observed potentially clinically significant (PCS) safety laboratory test values will be flagged and summarised. Length of menstrual cycle and C-SSRS scores will be summarised using descriptive statistics.

For variables that are heavily dependent on sex and age (such as Tanner and menstrual cycle length) further exploratory descriptions will be made.

Analyses will be performed with respect to the baseline in lead-in study 12709A or 12710A and Baseline Extension A.

For exploratory use a random effects slope and intercept model will be applied using Mixed Model Repeated Measurements (MMRM) to study long-term development in safety parameters such as weight.

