## 3 Endpoints

### 3.1 Primary Endpoint

Safety and tolerability:

- adverse events (AEs)
- PAERS assessment
- Tanner score
- absolute values and changes from OLEXA in clinical safety laboratory tests, vital signs, height, weight and ECG parameters
- length of menstrual cycle

- potentially clinically significant clinical safety laboratory test values, vital signs, weight, and ECG parameter values relative to OLEXA
- C-SSRS categorisation

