### **12.6.3 Tanner Evaluation**

Tanner staging is a scale for assessing physical development and sexual maturity during onset and progress of puberty. The scale includes five stages of pubertal changes (called Tanner stages) separate for males and for females.

For females, the 5 stages of maturation are recognized by assessing pubic hair and breast development. For males, the 5 stages of maturation are recognized by assessing pubic hair, growth of penis and testicles. Post-puberty is defined as a Tanner stage = 5 in both of observed criteria.

Shift tables for the Tanner evaluation displaying shifts from OLEXA to withdrawal/completion will be provided by sex, lead-in treatment and lead-in study, and include the numbers and percentages of patients.

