## 17 Changes to Analyses Specified in the Protocol

The following changes have been made as compared to the latest version of the protocol:

- C-SSRS categorisation has been updated and will no longer include C-CASA.
- Treatment emergent adverse events (TEAE) in 12712A is defined as an adverse event that starts or increases in intensity or seriousness after visit 1 of study 12712A.
- The analyses regarding time to first relapse and time to first loss of remission have been removed
- The analysis of random slope and intercept has been removed

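### Height, weight, LH, FSH and prolactin are tabulated with the sexes pooled and no allowance for growth or pubertal stage, so normal development drives these primary-endpoint summaries

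*SAP*

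**What the plan says.** SAP 3.1 makes "absolute values and changes from OLEXA in clinical safety laboratory tests, vital signs, height, weight and ECG parameters" part of the primary endpoint. The method for height and the hormones is the general one in SAP 12.2. Its content is "Descriptive statistics for the safety variables, both absolute values and change from baselines", and its layout is that "the tables will be presented for all patients and by lead-in study and by lead-in treatment". The section also plans counts of patients with "values out-of-reference range and/or PCS range will be summarized by variable, visit, and last post-baseline assessment". SAP 12.4, headed for vital signs and weight, describes only vital-sign summaries by visit and does not mention height.

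The hormone panel in Protocol 9.4.2 (Panel 4) reads "S-estradiol (girls) S-total testosterone (boys) S-LH S-FSH S-LHRH S-prolactin". Estradiol and testosterone are each confined to one sex; the other hormones quoted carry no sex restriction. The same section says the panel belongs to this study and is first drawn at its Visit 1.

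Protocol 17.10.2 contains a commitment: "For variables that are heavily dependent on sex and age (such as Tanner and menstrual cycle length) further exploratory descriptions will be made". The SAP acts on it in two places. In 12.6.3, "Shift tables for the Tanner evaluation displaying shifts from OLEXA to withdrawal/completion will be provided by sex, lead-in treatment and lead-in study". In 12.6.4, menstrual variables are summarised for girls. SAP 17 records that "The analysis of random slope and intercept has been removed"; Protocol 17.10.2 had named weight as an example for that model.

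**The concern.** These are developmental variables measured over 26 weeks in boys and girls aged 7 to 18. Some patients are prepubertal, some are in mid-puberty and some have nearly finished growing. Over half a year many will grow taller and heavier, and their gonadotropins will move, whatever drug they take. Every patient takes vortioxetine, so no concurrent arm shows what normal development would have been.

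A raw mean change then depends heavily on who was enrolled. Without a sex split, a stage split or an external growth standard, a reader of the report cannot tell whether a given mean reflects treatment or the mix of ages, sexes and pubertal stages. Height, weight and laboratory changes are part of the primary endpoint, and a separate blood kit is used for the hormones, so the tables should be able to inform the question for which the data are collected.

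**Working it through.** **1. The plan's own figure.** The only number the plan derives is the sample size (Protocol 17.12, SAP 15): 1200 randomised, 15-20% withdrawal, at most 85% rolling over.
- 15% withdrawal: 1200 × 0.85 × 0.85 = 867
- 20% withdrawal: 1200 × 0.80 × 0.85 = 816

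The stated figure of about 850 lies in this range. It is not in dispute and is used below only to judge cell sizes.

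**2. What is planned for each variable.**

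| Variable | Split by sex | Split by age or stage | Growth-standardised | PCS rule (SAP Appendix IV) |
|---|---|---|---|---|
| LH, FSH | no | lead-in study at most | not applicable | none |
| Prolactin | no | lead-in study at most | not applicable | one upper limit for both sexes |
| Height | no | lead-in study at most | no | none |
| Weight, BMI | no | lead-in study at most | no | change of 7% or more |
| Tanner stage | yes | the variable is itself the stage | not applicable | none |
| Menstrual cycle | girls only | lead-in study at most | not applicable | none |

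The SAP already uses age bands elsewhere: Appendix IV Table 5 gives blood pressure ranges for 7-9, 10-12, 13-17 and 18 years and over. Age-specific handling is therefore feasible within this plan.

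**3. Is there any comparison group?** Not during the extension. The by-lead-in-treatment tables allow a cross-sectional look at hormones at OLEXA, among lead-in completers and with the sexes pooled. No hormone change from the lead-in baseline is available from this panel, because it starts at Visit 1 of the extension.

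**4. Height illustration.** The velocities are assumptions: 6 cm/year for patients growing fast and 2 cm/year for those near maturity, that is 3 cm and 1 cm in 26 weeks.
- 30% growing fast, no drug effect: 0.3 × 3 + 0.7 × 1 = 1.6 cm
- 50% growing fast, growth slowed by 20%: 0.8 × (0.5 × 3 + 0.5 × 1) = 1.6 cm

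The pooled raw mean is the same in both cases. A z-score takes out the gain expected for each patient's age and sex.

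**5. Weight illustration.** SAP 3.1 defines PCS weight relative to OLEXA. A 7% rise in 26 weeks equals 14% of baseline weight per year: 4.2 kg/year at 30 kg and 8.4 kg/year at 60 kg. Assume a normal gain of 4 kg/year, which is 2 kg in 26 weeks:
- at 30 kg: 2 / 30 = 6.7%, almost at the flag
- at 60 kg: 2 / 60 = 3.3%, well below it

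With no drug effect, the count of high flags thus depends on the age mix. The low flag has the reverse weakness: a growing child who gains nothing over 26 weeks is not flagged.

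**6. Cell sizes for stratified hormone tables.** Two sexes by three Tanner groups is 6 cells, on average 850 / 6 ≈ 142 patients if evenly filled. Splitting also by the two lead-in studies gives 12 cells, averaging about 71, before any split by lead-in treatment. Real cells will be uneven, so all-patients tables are the sensible place for this stratification.

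**The case against.** Several stronger readings are tempting, and the documents do not support them.

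- **That ages 7 to 18 are pooled throughout.** Only the all-patients layout certainly does this. Patients turning 18 are mentioned only for 12710A, and Protocol 1.2 says children and adolescents should generally be studied separately. The by-lead-in-study tables therefore probably separate the two groups, although neither study's age range is stated. The sexes remain pooled within each, and adolescents alone still cover much of puberty.
- **That the plan is blind to disturbed puberty.** It has Tanner shifts by sex, menstrual data in girls, sex-specific estradiol and testosterone, and an adverse event search (SAP Panel 5) that includes delayed and precocious puberty and LH and FSH deficiency.
- **That only raw means are reported.** Out-of-range and PCS counts are planned, and listings carry sex and age. Laboratory reference ranges may be age- and sex-specific; the documents do not say. Neither device gives an expected growth for height.
- **That an age-adjusted weight model was dropped.** The random slope and intercept model was exploratory, no age or sex term was stated for it, and SAP 17 discloses its removal.
- **That the SAP breaches the protocol.** Protocol 17.10.2 gives Tanner and cycle length as examples, and the SAP covers both. Extending the commitment to hormones, height and weight is a natural reading, but those variables are not named.
- **That better tables would isolate a drug effect.** They would not. Pubertal progression within a Tanner group over 26 weeks remains mixed with any treatment effect.

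What remains is narrower: for these five variables no sex or stage split and no growth standard is planned, although most of the inputs are already collected.

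**Conclusion.** The point holds in this limited form. LH, FSH, prolactin, height and weight are described with the sexes pooled in every table and ages split at most by lead-in study. The weight and BMI flag makes no allowance for growth, and height has no flag. In a single-arm extension, expected growth, pubertal progression and sex mix therefore drive these parts of the primary endpoint. The SAP gives the protocol's promised further description only to Tanner stage and the menstrual cycle, and SAP 17 does not list that promise as withdrawn.

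The size cannot be fixed from the documents, which give no growth rates or hormone distributions. The 1.6 cm and 6.7% against 3.3% illustrations rest on assumed velocities, age mixes and baseline weights. They show that the ambiguity is as large as a 20% slowing of height growth under those assumptions, not that such an effect exists. The variables are only described, so no test or sample size is affected. The change is worth making because it improves interpretation of primary safety data at little cost.

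**What to change.** - **SAP 12.4:** add age- and sex-standardised z-scores for height, weight and BMI at each visit where they are measured, from one named growth reference covering the whole age range. Report change in z-score from OLEXA and, where measured, from the lead-in baseline.
- **SAP 12.2/12.3:** add tables of LH, FSH and prolactin (value and change from OLEXA) by sex and OLEXA Tanner group (1, 2-4, 5), for all patients only. State a rule for assigning one stage when a patient's Tanner criteria differ.
- **Keep** the raw summaries, the PCS counts and the existing Tanner and menstrual tables.
- **State the limit:** without a concurrent control, these tables reduce but do not remove confounding with normal development.

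The cost is SAP wording, a growth-reference lookup and a few more descriptive tables. Sex, age, Tanner stage, height, weight and the hormones are already collected, so no patients or procedures are added. The downsides are some small cells and the need to choose one growth reference for a multinational population.
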